1) Prospective, randomized multicenter trial. Approximately 159 randomized and 91 non-randomized patients would be recruited over 18 months with follow-up through 5 years.

2) Subjects (aged 45-80 years) with CSM (2 or more levels of spinal cord compression from C3 to C7) with 2 or more of the following symptoms/signs, clumsy hands, gait disturbance, hyperreflexia, up going toes, bladder dysfunction, or ankle clonus, will be treated with either ventral decompression/fusion, dorsal decompression with fusion, or dorsal laminoplasty. (Patients <45 years of age do not generally suffer from degenerative arthritis, which is why the lowest age of inclusion is 45).

3) Subjects with C2-C7 kyphosis $> 5^\circ$ (measured in standing neutral cervical spine radiograph), a segmental kyphotic deformity defined as 3 or more disc-osteophytes that extend dorsal to a C2-C7 dorsal-caudal line measured on cervical spine CT, structurally significant ossification of the posterior longitudinal ligament (OPLL), previous cervical spine surgery, or significant active health-related comorbidity (Anesthesia Class IV or higher) would be excluded from the study.

4) Each subject will be treated with either a Front Decompression/Fusion or Back of the Neck Decompression with fusion or Laminoplasty as part of standard clinical care. Decompression of the spinal canal to a diameter of at least 13 mm with restoration of cerebrospinal fluid flow around the spinal cord will be the goal, regardless of the approach. Surgical techniques have been standardized. Back of the neck decompression with fusion and laminoplasty are equivalent and preliminary evidence suggests that the outcomes are similar using the SF-36 PCS, which is the same questionnaire being used in this study (see table in Power Analysis section below).

5) Functional outcomes will be determined using well-known quantitative scales (SF-36, Oswestry Neck, mJOA, and EuroQol-5D). These instruments will be administered pre-op, 3 months, 6 months, and at 1 year. Additionally, functional outcomes instruments (SF-36, Oswestry Neck, and EuroQol-5D) will be collected annually at years 2,3,4 and 5.

6) Two independent neuroradiologists will review post-operative imaging at 3 months, and 1 year. Post-operative cervical spine MRI will be performed at 3 months to document satisfactory spinal cord decompression. Cervical spine

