flexion-extension radiographs will be obtained pre-operatively on all patients and at one year after surgery to assess cervical fusion and/ or radiographic complications. Standing cervical-thoracic-lumbar-sacral films will be obtained on all patients pre-operatively and at one year postoperatively (post-operatively in the randomized group only) to assess cervical as well as overall sagittal balance. A cervical spine CT will be obtained on patients at 1 year who have an NDI score > 30 or whose plain films suggest instability.

7) A study coordinator will collect data at 30 days and at 1 year to document any complications or re-operations. Additionally, the study coordinator will assess whether the patient is having any swallowing complications following surgery.

8) Health resource utilization information (including out-of-pocket expenses) will be obtained using patient diaries along with copies of all medical bills and receipts at 1 month, 3 months, 6 months, and 12 months post-operatively for all of the patients. Participants also will be asked to keep track of days missed from work and days unable to perform usual activities, in addition to days missed from work for medical treatments or evaluations.

F. Data and Safety Monitoring Plan

- 1) All serious unexpected adverse events (e.g. death within 30 days of operation) will be reported to the IRB within 24 hours. Any appropriate funding agencies or regulatory agencies would be notified as well.
- 2) Any serious anticipated adverse event (e.g. wound infection, pulmonary embolus) will be reported to the IRB whenever their magnitude or frequency exceeds expectations.
- 3) All other adverse events (including loss of privacy, significant economic harm) will be reported to the IRB on an annual basis or at the time that re-approval is sought. Any adverse event judged unlikely or unrelated to the study will also be included in an annual report for the IRB.

G. Statistical Considerations

a. Specific data variables being collected for the study.

The data collection sheets will be submitted along with this protocol. There will be several data sheets as follows:

- 1) Screening/Baseline, 1 Month, 3 Months, 6 Months, and 1 Year Visit Checklist
- 2) Informed Consent Process
- 3) Inclusion/Exclusion Criteria
- 4) Baseline Demographics
- 5) Spine surgeon's data sheet

- 6) 30-day and 1 Year morbidity data sheet
- 7) 1 Month, 3 Months, 6 Months, 1 Year Return to Work Status
- 8) 3 Month Swallowing Evaluation

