The research team has extensive experience conducting economic evaluations, including assessment of musculoskeletal interventions alongside RCTs and will conduct the proposed patient-oriented health resource utilization analysis. We will collect health resource utilization data as well as health cost data alongside this RCT.

Cost Analysis

Costs will be estimated for each patient from a societal perspective from the sources listed below, including only patients from the United States. A one-year time horizon will be selected to align with the primary outcome measure of the CSM-S Trial.

A. Index Hospitalization Costs:

- Hospital Costs: Total hospital charges (TotalHC) will be used to estimate costs using hospital-specific and year-specific Medicare cost-to-charge ratios (CCR). The costs will be adjusted for inflation to the current year without a 3% discount.
 - As a sub-analysis, hospital charges for specific revenue-centers (i.e., radiology, pharmacy, physiotherapy and occupational therapy) will be converted to costs using hospital-specific and year-specific Medicare CCRs. This will allow the identification of the major drivers of the difference in cost between the surgical strategies. A crosswalk between the revenue center and the cost center will be created.
- For professional services (identified with either HCPCS code or CPT-4 codes) provided to patients during the index hospitalization, costs will be calculated using national reimbursement amounts from the appropriate Medicare fee schedules for the respective year and site.

B. One-Year All-Cause Costs:

- One-year total hospital charges will be utilized in this part of the analysis. These include major health resource utilization events in the year following surgery including readmission, reoperation, injections, advanced imaging, and physical therapy.
 - Year-specific, site-specific Medicare cost-to-charge ratios, will be used to determine one-year costs from charges. These costs will be inflation adjusted. Professional services will also be included (identified with either HCPCS code or CPT-4 codes) and costs will be calculated using national reimbursement amounts from the appropriate Medicare fee schedules for the respective year and site.

C. Costs Due to Lost Productivity:

- We will assume that work was halted for patients on the procedure date.

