- The ICER will be calculated in a three-way extended dominance analysis, comparing each surgical treatment to the others. If a surgical procedure is both less costly and provides higher QALYs gained, that treatment will be dominant

over the others.

- A comparison of anterior and posterior approaches (namely, grouping the two posterior procedures) will be performed independently from the ICER model.
- Probabilistic analysis will be performed to account for sampling variation around ICER point estimates.
- Cost/QALY gained will be reported for each surgical treatment and for each approach.

d. Power Analysis.

Sample size for Specific Aim #1a (Ventral surgery is associated with superior SF-36 PCS outcome at one year compared to dorsal (fusion or laminoplasty surgery):

Sample size estimates were calculated based on analysis of covariance model with $\alpha = 0.05$ at 80% and 90% power using Power Analysis and Sample Size software (PASS 2008, NCSS, LLC. Kaysville, Utah). The primary endpoint is the SF-36 PCS. This component of the SF-36 is derived from the sums of scores of 21 items and thus exhibits distributional behavior commensurate with assumptions for parametric analysis. Our preliminary data suggest standard deviations for SF-36 PCS between 10 and 12 and correlations of baseline with one year SF-36 PCS between 0.6 and 0.7. *The following table describes the total sample size (2:3 ventral-dorsal randomization) required to detect a five point difference in SF-36 PCS one year post-surgery for various combinations of power, standard deviation and one year correlations under a fixed design.*

A minimum sample size of **137** patients provides at least 90% power (see Tables below):

Surgery (N)	Pre-op	Post-Op	Correlation between Pre- and Post-Op	Difference
Ventral (45)	35.5 ± 10.3	44.2 ± 11.7	0.64	+ 8.7 ± 8.2
Dorsal (70)	35.8 ± 11.3	39.8 ± 11.6	0.66	+ 4.0 ± 9.5
Dorsal Fusion (42)	35.0 ± 11.7	39.6 ± 12.4	0.65	+ 4.6 ± 10.0
Laminoplasty (28)	37.0 ± 10.9	40.1 ± 10.6	0.67	+ 3.1 ± 8.8
All patients (115)	35.7 ± 10.9	41.5 ± 11.8	0.64	+ 5.8 ± 9.7

Difference / SD	Correlation	80% Power / 5% Type I error (2-sided)			90% Power / 5% Type I error (2-sided)		
		N _{Ventral}	N _{Dorsal}	N	N _{Ventral}	N _{Dorsal}	N

5 / SD = 10	0.60	38	56	94	50	74	124
5 / SD = 10	0.65	40	59	99	53	78	131
5 / SD = 10	0.70	42	62	104	55	82	137

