Exclusion Criteria: Any of the following: C2-C7 kyphosis $> 5^\circ$ (measured in standing neutral cervical spine radiograph), segmental kyphotic deformity (defined by ≥ 3 osteophytes extending dorsal to a C2-C7 dorsal-caudal line measured on cervical spine CT), structurally significant ossification of posterior longitudinal ligament (OPLL – measured on cervical spine CT), previous cervical spine surgery, or significant active health-related co-morbidity (Anesthesia Class IV or higher).

EXCLUDE

INCLUDE

**Segmental-Cervical
Kyphotic Deformity**

Yes

No

Figure. Two cases with sagittal CT reconstructed images are depicted. A line is drawn from the dorsal caudal point of C2 to the dorsal caudal point of C7. If 3 or more levels of disc-osteophyte extend dorsal to the line, then the case has a segmental-cervical kyphotic deformity and the case would be excluded from the study. The C2-C7 Cobb angle is 5 degrees lordosis in both cases

Subjects will be enrolled by participating spine surgeons who are investigators in the study. These subjects will be identified within the existing practice of each surgeon. There will be no advertising or any effort to recruit subjects into the study from outside the practice of a study surgeon investigator.

Once a patient has been screened, identified as having CSM, and agreed to participate in the trial by signing consent, the subject will undergo two reviews. The patient's images will first be reviewed by a Central Review Committee ([name] and [name]) to confirm eligibility. If the patient is deemed eligible, their images will then be reviewed by the spinal experts network. The patient's images will be uploaded onto the web-based platform, and an email will be generated and sent to all 15 members (15 CSM surgeon investigators) of the spinal experts panel. Each surgeon will be asked to vote: 'randomize' or 'do not randomize' and then to characterize his/her preferred surgical approach as **ventral** or **dorsal**. If after 72 hours, a majority (>50%) of the review panel (with at least 9 votes for a quorum) favor randomization (equipose) and less than 80% select one approach (ventral or dorsal) over another, then the patient will be eligible for study randomization.

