The results of the voting (the number of votes randomize or do not randomize and the number of ventral or dorsal votes) will be available to the patient both to increase patient trust and confidence in the recommendation for randomization, as well as to protect patients from undergoing randomization when one approach (ventral or dorsal) might be superior for that patient.

Patient Randomization (See Figure 1 Below)

[figure not shown]
Patients will be offered randomization in a subsequent one-hour meeting (following spinal experts review of the case) among study coordinator, surgeon, and patient if two conditions are met:

- 1) Central Review Committee ([name] and [name]) checked the images and clinical exam findings and found the patient eligible; and
- 2) Spinal Experts Panel confirmed patient's eligibility (>50% majority vote "randomize" and less than 80% select one approach (ventral or dorsal) over another).

The patient can either consent to or decline randomization. There will be two categories of patients who have signed an IRB-approved consent to participate in the study:

1. Randomized cohort: Upon confirmation of eligibility and patient acceptance of randomization, the study coordinator will access the assignment by logging into the secure website (<https://pip.acesis.com>) with a password and will obtain the randomization assignment from the web-based platform with its pre-programmed blocked (2, 4, or 6 subjects/block) stratified site-specific randomization scheme. Randomized patients will be followed for five years.
2. Non-Randomized cohort: The non-randomized cohort will consist of all patients who meet entry criteria but for whom equipose is not confirmed by spinal experts panel. It also will consist of patients who do not consent to randomization. All non-randomized patients will be asked to complete all the study questionnaires and will be followed for five years. The non-randomized cohort will not have an independent radiologist evaluation.

Figure 1 Randomization Procedure

B. Source of Research Material

Subjects will be identified from within the practice of spine surgeon investigators.

C. Consent Procedures

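### The cost-effectiveness plan limits its population only to US patients and groups them by procedure, so it permits a ventral-versus-dorsal comparison that pools randomised with non-randomised patients

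*Combined protocol and SAP*

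**What the plan says.** All references are to the combined protocol and SAP.

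- **Population for costs** (II.G.c, Cost Analysis): "Costs will be estimated for each patient from a societal perspective from the sources listed below, including only patients from the United States". No other restriction follows.
- **Framing of the economic work** (II.G.c, Analysis Plan for Cost-Effectiveness): "We will collect health resource utilization data as well as health cost data alongside this RCT".
- **Comparisons** (II.G.c, ICER): a three-way analysis of the surgical treatments, and separately: "A comparison of anterior and posterior approaches (namely, grouping the two posterior procedures) will be performed independently from the ICER model".
- **Adjustment** (II.G.c, Cost Analysis, statistical paragraph): the Gamma GLM for cost adjusts for baseline characteristics found to be imbalanced. The section on utilities and QALYs describes imputation and interpolation but no adjustment, and does not repeat the US limit.
- **Who supplies the data**: diaries, bills and receipts are obtained "at 1 month, 3 months, 6 months, and 12 months post-operatively for all of the patients" (II.E, item 8). For the questionnaires, which include the EQ-5D: "All non-randomized patients will be asked to complete all the study questionnaires and will be followed for five years" (III.A, Patient Randomization).
- **Who is non-randomised** (III.A, Patient Randomization): "The non-randomized cohort will consist of all patients who meet entry criteria but for whom equipose is not confirmed by spinal experts panel". Patients who refuse randomisation join the same cohort.
- **Screen before randomisation** (III.A): a majority of the expert panel must "favor randomization (equipose) and less than 80% select one approach (ventral or dorsal) over another, then the patient will be eligible for study randomization".
- **Planned size** (II.E, item 1): "Approximately 159 randomized and 91 non-randomized patients would be recruited over 18 months with follow-up through 5 years".

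**The concern.** Randomised arms exist for ventral versus dorsal surgery, and the primary SF-36 PCS analysis uses them: Statistical Methods in II.G.c commits the primary analyses to all randomised subjects by intent-to-treat. The economic plan carries over neither the population nor the grouping. A team following it could compare everyone operated on ventrally with everyone operated on dorsally.

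For non-randomised patients, the approach is not allocated by chance. Where the panel did not confirm equipoise, features of the case that shaped the vote may also bear on which operation was done and on later cost and quality of life. Where the patient declined, patient or surgeon preference may play the same part. Either way, a cost or QALY difference could reflect who received each operation and not what the operation did. The resulting cost per QALY would also describe a different population from the clinical result beside which it will be read.

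**Working it through.** **1. The planned numbers.** Power Analysis (II.G.d) starts from 137 patients and inflates by 5% and then 10%: 137 × 1.05 × 1.10 = 158.2, rounded up to 159. The plan's figure reproduces. With the 91 non-randomised patients, the total is 159 + 91 = 250.

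**2. Share of a pooled set that is non-randomised.** 91 / 250 = 0.364, or 36.4%. If the set is limited to randomised patients, the share is 0%.

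**3. Effect of the US limit.** The documents do not give the US share. Assume it lies between 60% and 100% in each cohort:

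- All randomised and 60% of non-randomised patients in the US: 54.6 / (159 + 54.6) = 25.6%.
- 60% of randomised and all non-randomised patients in the US: 91 / (95.4 + 91) = 48.8%.
- Equal US shares: 36.4%, whatever the share.

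**4. Share without panel-confirmed equipoise.** The split of the 91 is not stated. At planned numbers these patients could be 0 / 250 = 0% to 91 / 250 = 36.4% of a pooled set.

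**5. Which set does the text point to?**

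- Towards all enrolled patients: costs for each patient, limited by country alone; the zero-cost rule, which counts the whole study population; and grouping by procedure.
- Towards randomised patients: the description of data collection as running beside an RCT.
- Neutral: the GLM paragraph's word for the groups it compares is cohorts. Because it promises a mean predicted cost for each, surgical groups are the likelier meaning, not randomised versus non-randomised.
- Contrast: the Year 2 plan names its sets (the two randomised groups, and as-treated groups). The cost plan names none.

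**6. Grouping.** Randomisation is described only as ventral versus dorsal, 2:3 (II.G.d). Three procedure groups cannot all be assigned arms. The two-way contrast is then built by merging the two dorsal procedure groups, not by returning to the assignment.

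**7. How a case-mix gap would pass into the QALY difference (illustration only).** The plan interpolates utility linearly between baseline, 3, 6 and 12 months. The weights, in years, are:

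- baseline 0.25/2 = 0.125
- 3 months (0.25 + 0.25)/2 = 0.25
- 6 months (0.25 + 0.5)/2 = 0.375
- 12 months 0.5/2 = 0.25

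Assume a case-mix utility gap of 0.05 between non-randomised ventral and dorsal patients, and the same ventral:dorsal split in both cohorts:

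- Gap at 12 months only: 0.25 × 0.05 = 0.0125 QALY in that cohort; × 0.364 = 0.0046 pooled.
- Gap at every visit including baseline: 1 × 0.05 = 0.05; × 0.364 = 0.018 pooled.
- Over the shares in step 3: 0.0125 × 0.256 = 0.003 to 0.05 × 0.488 = 0.024.

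The 0.05 is assumed; nothing in the documents supports a particular value or sign.

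**The case against.** The strongest reply is that nothing in the documents says the cohorts are pooled. The economic data are described as collected beside an RCT, and the one-year horizon is chosen to match the trial's primary outcome. Collecting diaries and EQ-5D from everyone does not define an analysis set either: SF-36 is also collected from non-randomised patients, yet the primary analysis uses only randomised ones. This stands. A reader might infer that the plan does pool the cohorts; the text supports only that it permits this and does nothing to prevent it.

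A second reply also stands. A reader might infer that the non-randomised patients were all steered to one approach by their anatomy and have no counterparts in the other group. The documents do not say so. The cohort includes decliners; equipoise can go unconfirmed because the vote to randomise lacked a majority or a quorum; and nowhere is it said that these patients receive the approach the panel preferred. The votes are only made available to the patient.

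Third, the three-way ICER cannot lose a protection it never had, since no random assignment between dorsal fusion and laminoplasty is described. The loss concerns the two-way comparison.

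Fourth, the plan does adjust for imbalanced baseline characteristics. This answers only part of the point. The adjustment is stated for costs and not for QALYs, and it names neither randomisation status nor the panel vote.

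**Conclusion.** The point holds as a gap in specification. The cost-effectiveness population is limited by country alone and grouped by procedure, so the plan permits a ventral-versus-dorsal comparison outside the randomised arms. A pooled set would be 36% non-randomised at planned numbers, or 25.6% to 48.8% under assumed US shares of 60% to 100% per cohort. The pooled cost and QALY differences would then be exposed to confounding by indication.

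The documents establish neither the size nor the direction of any bias. A reader might infer that it could reach about 60% of a plausible QALY effect (0.018 / 0.03 = 61%). That takes an assumed true difference of 0.03 and an assumed gap of 0.05 at every visit, baseline included. With the same gap at 12 months only, the figure is 0.0046 / 0.03 = 15%. Neither is a finding about this trial.

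This is a secondary analysis, and the primary PCS comparison is unaffected. It is worth correcting because the result will be read as trial evidence and a randomised comparison is available from data already planned.

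**What to change.** In II.G.c, Analysis Plan for Cost-Effectiveness:

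1. Make the main ventral-versus-dorsal comparison of cost, QALYs and cost per QALY in US randomised patients, by assigned arm.
2. Use the same patient set for costs and QALYs. At present the US limit is stated for costs only, so the two parts of the ratio could come from different patients.
3. Report any result in all enrolled US patients as a sensitivity analysis.
4. Label the three-way ICER as observational, whichever cohorts it uses.

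Restricting the three-way analysis to panel-confirmed equipoise, or adjusting it for the panel's vote share, is a matter of judgement and is not needed to close this gap.

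The change is to SAP wording and needs no new data. It costs precision in the ventral-versus-dorsal comparison: at most 159 patients instead of 250 before the US limit. With equal US shares, equal variance and the same ventral:dorsal split, intervals widen by a factor of √(250/159) = 1.25.

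### The index-stay cost-driver sub-analysis covers four revenue centres only, so it cannot identify a driver that lies in any other part of the hospital bill

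*Combined protocol and SAP*

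**What the plan says.** The relevant text is in Section II.G.c, Analysis Plan for Cost-Effectiveness, Cost Analysis.

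- **Main index cost (part A).** The whole hospital bill is the starting point: "Total hospital charges (TotalHC) will be used to estimate costs". The Medicare cost-to-charge ratios (CCRs) used are described as varying by hospital and year.
- **Sub-analysis (part A).** "hospital charges for specific revenue-centers (i.e., radiology, pharmacy, physiotherapy and occupational therapy) will be converted to costs", with CCRs described in the same terms. The stated purpose is: "This will allow the identification of the major drivers of the difference in cost between the surgical strategies". The bullet ends: "A crosswalk between the revenue center and the cost center will be created".
- **One-year cost (part B).** "Year-specific, site-specific Medicare cost-to-charge ratios, will be used to determine one-year costs from charges".
- **Professional services (parts A and B).** These stay outside the CCR method: "costs will be calculated using national reimbursement amounts from the appropriate Medicare fee schedules for the respective year and site".
- **Use of the costs.** They are added to lost productivity to give total societal cost, and then: "The ICER will be calculated in a three-way extended dominance analysis, comparing each surgical treatment to the others".

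Nowhere does the cost section name operating room, implants or supplies, or room and board.

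**The concern.** The stated aim is wider than the stated scope. The list follows *i.e.*, which makes it exhaustive, and four centres cannot show which parts of a whole bill drive a difference in its total. A driver in an unlisted centre would be missed, and a reader given only the four results could take the largest of them for the main driver.

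Two of the three strategies are fusions and one is a laminoplasty. It is natural to expect them to differ in implants, operating time and length of stay, and none of these corresponds to a listed centre. That expectation is a subject-matter assumption, since the documents compare the procedures on none of the three. The mismatch between scope and purpose does not depend on it.

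What is at stake is the explanation of any cost difference that the trial reports, which surgeons and payers would use to judge whether the difference applies to them.

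**Working it through.** The documents give no charge, CCR or cost split, so there is no figure of the plan to reproduce. The check is of scope, followed by arithmetic on assumed values.

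**1. Notation.** For two strategies, let d_k be the difference in charges in revenue centre k and r_k the CCR for that centre. Let L be the four listed centres, U all the others, and r a single ratio for one hospital and year.

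**2. What the sub-analysis can see.** With centre-level ratios the cost difference is

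D = Σ_L r_k·d_k + Σ_U r_k·d_k.

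The plan reports terms from the first sum only. Take an assumed charge difference of $10,000 in one unlisted centre and a ratio of 0.30. It adds 0.30 × 10,000 = $3,000 to the total and $0 to every component reported.

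**3. Share out of reach.** If the listed centres hold a share s of hospital cost, the rest is 1 − s.

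| Assumed s | Outside the sub-analysis |
|---|---|
| 0.10 | 0.90 |
| 0.20 | 0.80 |
| 0.30 | 0.70 |
| 0.50 | 0.50 |

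This is a share of cost, which need not equal the share of the between-strategy difference.

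**4. Whether the parts add up to the total.** The main bullet and the sub-analysis describe their CCRs in the same words, but only the sub-analysis has the crosswalk. Two readings are open.

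- *Centre-level ratios in the sub-analysis, one ratio r for the total.* Total minus listed parts is then r·Σ_U d_k + Σ_L (r − r_k)·d_k. The second term is an artefact of mixing scales. With r = 0.30 and $10,000 in a listed centre, it is (0.30 − 0.15) × 10,000 = +$1,500 if r_k = 0.15, and (0.30 − 0.50) × 10,000 = −$2,000 if r_k = 0.50.
- *The same ratio in both.* The parts add up, but the sub-analysis only rescales charges and the crosswalk has no costing role.

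The plan does not say which is meant.

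**5. Why the ratio level deserves a sensitivity analysis.** Suppose one strategy has $10,000 more implant and operating-room charges (ratio 0.20) and the other $5,000 more bed-day charges (ratio 0.45). A single ratio of 0.30 gives 0.30 × (10,000 − 5,000) = +$1,500. Centre ratios give 0.20 × 10,000 − 0.45 × 5,000 = 2,000 − 2,250 = −$250. If all centre ratios equal 0.30, both methods give +$1,500. All these inputs are assumed. The example shows that the level can matter, not that it does here.

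**The case against.** The strongest reply is that nothing is left out of the cost that enters the ICER. Operating-room, implant and room charges on the hospital bill are part of total hospital charges. The four-centre list limits a descriptive sub-analysis that no later step uses. Because the total is costed too, a large difference that the four centres do not explain would show as a remainder.

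Most of this stands. The total is not truncated, and how the authors would word their findings cannot be predicted. But a remainder shows only that the driver lies elsewhere and does not say where. The plan does not promise to report one, and it is clean only if total and parts share one CCR scale.

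A reader might go further and infer that the base case applies one hospital-wide ratio to all departments, and that the ICER is therefore distorted. The documents do not support that. They index the ratios by hospital and year and never state the level at which they apply. One ratio per hospital and year is a natural reading, but an inference. It would not be one ratio for the whole trial, and professional fees are costed separately. No charge or ratio is given from which a distortion could be sized or signed.

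Nor do the documents show that centre-specific ratios should replace the base case. Hospitals without itemised charges would stay on another method. The Power Analysis describes randomization between ventral and dorsal surgery, not between dorsal fusion and laminoplasty. If that second choice varies by site, mixed costing could itself bias the three-way comparison.

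**Conclusion.** The point holds for the sub-analysis. As written, it cannot identify a cost driver in any unlisted revenue centre, so it cannot support the purpose stated for it. This follows from the text alone. The 70-90% lying out of reach rests on an assumed 10-30% share for the four centres, and the belief that implants, operating time and stay separate the procedures is likewise an assumption.

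On the main cost estimate the finding is narrower: the level of the CCR is not stated, and no check on it is planned. The probabilistic analysis is described as addressing sampling variation, which is a different matter. The effect on the ICER is of unknown size and direction. The consequence is confined to secondary economic results. The point is worth correcting before the cost analysis is run, because the remedy is cheap.

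**What to change.** 1. Extend the planned crosswalk to every revenue centre on the index bill, naming implants and supplies, operating room and anaesthesia, and room and intensive care alongside the four already listed.
2. Report the between-strategy difference by centre, with a remainder line for charges that cannot be assigned, so that the parts sum to the total on one stated CCR scale.
3. Keep the total-charge method as the base case, and state the level at which its ratio is applied, for both the index stay and the one-year costs.
4. Add centre-specific costing as a sensitivity analysis where itemised charges exist, and report how many patients per strategy and site it covers, so that any imbalance in coverage is visible.

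The cost is additional coding of bills. The sub-analysis already needs charges split by revenue centre, and the added centres lie within the total charges already to be collected. Whether every hospital can supply an itemised bill for all centres is not stated, which is why the remainder line is needed and why step 4 is a sensitivity analysis. If the wider coding is not feasible, the fallback is to drop the claim about major drivers and describe the sub-analysis as a report on four selected centres.
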